9.5.2 Safety monitoring committee (SMC)

An independent SMC composed of three independent individuals will be appointed. The SMC will include an independent local safety monitor, and two independent experts nominated by the PI. A PATH representative is allowed as an observer on the SMC, and is promptly informed of any safety concerns that have been raised by the SMC or have been raised to the SMC for their advice or review, and of their response.

The SMC will be established for the purpose of monitoring the study and to provide independent, non-binding advice on safety and ethics. The responsibilities and procedures of the SMC members are defined in the SMC Charter.

9.5.3 Review of safety data by the safety monitor and SMC

Safety Meetings

The SMC will review safety data at pre-defined time points throughout the study, specifically: upon completion of ≥ 7 days of post-administration follow-up in all subjects in a given dose-group (prior to commencing the first administration in the subsequent dose group). The chair of the SMC will determine for each time point whether a meeting will be held, or whether a recommendation from all members may be formalized through e-mail. The frequency of these reviews may be adapted upon SMC recommendation if deemed necessary. In addition, safety data for all participants will be assessed by the SMC at the end of the study. An ad hoc SMC meeting may be convened at any time or at the request of the PI or local safety monitor to review safety data from subjects and/or groups who meet any of the holding rules as specified in the protocol (9.5.4) and SMC charter.

Safety Reports

Safety reports will be prepared by the clinical investigator for review by the committee prior to each review. These reports will provide at a minimum the following information:

- Accrual data and subject status data with regard to completion of/discontinuation from the study.
- Summaries of solicited AEs, classified by severity.
- Unsolicited AEs (including SAEs), categorized by ICD-10 coding, severity and relatedness to study vaccine.
- Safety laboratory test results outside of normal institution reference ranges and considered clinically significant, classified by severity grading scale (irrespective of whether assessed as AEs).
- Any new or updated AEs that have met the holding rules.

The SMC will review the safety data within 2 working days. The SMC will summarize their recommendations to the study Sponsor as to whether there are safety concerns and whether the study should continue without change, be modified, or be terminated. If at any time a decision is made to permanently discontinue administration of study TB31F administrations in all subjects, the Sponsor will notify the METC and PATH expeditiously.

The advice(s) of the SMC will only be sent to the Sponsor of the study. Should the Sponsor decide not to fully implement the advice of the SMC, the Sponsor will send the SMC advice to the METC, including a note to substantiate why (part of) the advice of the SMC will not be followed.

Within-group progression

Subjects within a dosage group are to receive a single TB31F administration following a schedule, such that the first subject (sentinel) in each group will be administered mAb TB31F and observed for the occurrence of any AEs. The 2nd subject in each dose group will receive their dose of TB31F no sooner than 2 days after the first subject has received TB31F. For group 1, each remaining subject will receive their TB31F dose no sooner than 2 days after the previous subject. For groups 2-5, the remaining three

subjects in each dosage group will receive their TB31F dose no sooner than 2 days after the second subject has been administered TB31F. For the three remaining subjects in each dosage group, there will be at least a one hour interval in administration of TB31F between the completion of TB31F administration in one subject before the next subject is administered TB31F. On condition no holding rules are met (see below), administration of TB31F to all subjects within each dosage group will continue without any external (SMC) review. If a holding rule is met, administration of TB31F drug product will be held for all remaining subjects in that dosage group until the SMC has completed its review and made a recommendation on trial progress.

Inter-group progression

Progression to the next dosage group will depend in all cases upon a positive review by the SMC of safety data of the previous dosage group. The data to be reviewed before each dose group includes the safety data (solicited and unsolicited AEs through day 7 post TB31F administration) and clinically significant laboratory tests collected at 1, 2 and 7 days following TB31F administration for all subjects in the specified dose group. The SMC will review the AEs (local, general, and laboratory) and will make recommendations regarding the continuation of the study for each group.

9.5.4 Safety holding rules

The study may be placed on safety hold at any time for the following reasons:

- On advice of the safety monitor;
- On advice of the Principal/Clinical investigators;
- On advice of the SMC;
- On advice of the accredited METC;
- If holding rules are met (see below).

Holding rules for within-group progression:

If either of the first two subjects within a group meet a holding rule (see below), administration of TB31F will be held for all remaining subjects in that dosage group (and subsequent groups). The following stopping rules apply to subjects within a group:

- One or more participants experience a SAE that is determined to be at least possibly related to the administration of TB31F
- Two or more subjects experience a grade 3 adverse event (local, clinical systemic or laboratory systemic) possibly, probably or definitely related to TB31F administration and persisting at grade 3 for >48 hours

The study site member first aware of the event meeting the holding rule will notify the Principal Investigator and the Local Safety Monitor. The PI will alert the appropriate parties. The SMC will be notified within 24 hours. An ad hoc SMC review will be performed. The following considerations must be discussed:

- Relationship of the AE or SAE to the study product
- Relationship of the AE or SAE to TB31F dose
- If appropriate, additional screening or laboratory testing is provided to other subjects to identify subjects who may develop similar symptoms
- If any study related SAE is not listed on the current informed consent form (ICF), the PI will revise the ICF and subjects will be asked to provide consent on the new ICF

TB31F administration to subjects within the affected group and to the next higher dosage group may resume only if the local safety monitor, PI, SMC and the sponsor agree it is safe to resume TB31F administration. If the accredited METC has recommended safety hold, re-initiation of the study will require METC concurrence. The accredited METC and PATH REC will be informed of a safety hold by the sponsor. Following discussion, it may be decided to terminate the study.

All subjects who have received the study product will be followed for safety until resolution or stabilization (if determined to be chronic sequelae) of their AE(s). If at any time a decision is made to discontinue administration of study product in all subjects, expeditious notification will be provided by the Sponsor to the METC within 48 hours. The PI, local safety monitor, SMC, METC or PATH may stop or suspend the use of this product at any time.

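### The protocol's two mandatory hold sentences differ in trigger and reach, so no sentence clearly requires group 5 to pause if subject 3, 4 or 5 of fully dosed group 4 meets a holding rule

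*Protocol*

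**What the plan says.** Four pieces of text in the protocol govern a hold.

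- **9.5.4, mandatory, reaches later groups.** The trigger is "If either of the first two subjects within a group meet a holding rule". The consequence is that "administration of TB31F will be held for all remaining subjects in that dosage group (and subsequent groups").
- **9.5.3, within-group progression, mandatory, own group only.** "If a holding rule is met, administration of TB31F drug product will be held for all remaining subjects in that dosage group". The sentence before it reads "On condition no holding rules are met (see below), administration of TB31F to all subjects within each dosage group will continue".
- **9.5.4, study-level hold, permissive.** "The study may be placed on safety hold at any time for the following reasons"; a met holding rule is one of the reasons listed. The section ends: "The PI, local safety monitor, SMC, METC or PATH may stop or suspend the use of this product at any time".
- **9.5.4, resumption clause.** Dosing in the affected group and in the next higher dosage group may restart only when the local safety monitor, the PI, the SMC and the sponsor agree.

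There are two holding rules. One is met by a single subject with a serious adverse event at least possibly related to TB31F. The other begins "Two or more subjects experience a grade 3 adverse event" and also requires relatedness and persistence at grade 3 beyond 48 hours.

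Some matters are settled. A group that has not started needs a positive SMC review of data through day 7 (sections 3 and 9.5.3). A met rule leads to SMC notification within 24 hours and an ad hoc SMC review (9.5.4). The sponsor must suspend the study if there is sufficient ground to think subjects are at risk (9.1).

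**The concern.** The sentence with the wide reach has a narrow trigger, and the sentence with the wide trigger has a narrow reach. The case that falls between them is an event in subject 3, 4 or 5 of group 4, after the day-7 SMC review has released group 5 and while group 5 is part-way through dosing.

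At stake is whether site staff must stop or may stop. In group 5 the last three doses may be given one hour apart (Table 2), so staff need a single reading in advance. In a first-in-human study, a holding rule should not leave this to inference.

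**Working it through.** The plan gives no figure on this point, so there is none to reproduce. The check is a reading of the sentences against one scenario, with simple counts and dates.

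**1. Apply each sentence to the scenario.** Subject 3, 4 or 5 of group 4 has a related serious adverse event; all of group 4 has been dosed; group 5 is in progress.

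| Text | Triggered? | Reaches group 5? |
|---|---|---|
| 9.5.4, first-two-subjects sentence | No | Would, if triggered |
| 9.5.3, any-subject sentence | Yes | No; it covers group 4, where nobody is left to dose |
| 9.5.3, condition that no rule is met | Arguably | Unclear; it stands under within-group progression, and the next sentence refers to the same group |
| 9.5.4, study-level hold | Yes | Yes, but optional |
| 9.5.4, power to suspend | Available | Yes, but optional |
| 9.5.4, resumption clause | Yes | It presupposes a pause, but names the next higher dosage group |
| 9.1, sponsor suspension | Only on a judgement of sufficient ground | Yes, if so judged |

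The SMC gate between groups does not help, because group 5 has already passed it. SAP, Statistical interim analyses and stopping guidance, likewise speaks of evaluation before moving to the next group.

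**2. Does group 5 fit the resumption clause?** Protocol 6.5 puts 100 mg at 1.1 to 2 mg/kg for subjects of 50 to 90 kg (100/90 = 1.1; 100/50 = 2) and expects it to approximate 1 mg/kg IV. Group 4 received 10 mg/kg. Group 5 is the next group, but not a higher dose.

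**3. How much of each rule lies outside the 9.5.4 trigger?**

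- Related serious event: subjects 3, 4 and 5, so 3 of 5.
- Grade 3 rule: possible pairs in a group of five, C(5,2) = 10. Both in the first two: 1. Exactly one in the first two: 2 × 3 = 6. Neither: C(3,2) = 3. No single subject can meet this rule, so how the trigger applies to the 6 mixed pairs is itself unclear.

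These are counts of positions, not probabilities of events.

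**4. Is the overlap permitted?** Take the Table 2 minimum intervals, with the first group 4 dose as day 0. Group 4 is dosed on days 0, 2 and 4 (last three subjects on day 4). Group 5 may start 14 days later, on day 18, and continue on days 20 and 22. Group 4 subjects 3 to 5 are then at their own day 14 (18 − 4) when group 5 starts and day 18 (22 − 4) when it ends. That is past the day-7 review data and well inside the follow-up of about 84 days. The documents give only the minimum interval, not the actual dates.

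**5. Is there time for the SMC to act first?** Suppose the rule is met just after group 5 subject 2 is dosed. Subjects 3 to 5 may be dosed from 48 hours later, within about 2 hours of each other. SMC notification may take up to 24 hours. If the two-working-day review period in 9.5.3 also applies to ad hoc reviews (an assumption), the recommendation could come after all three doses unless someone chooses to pause.

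**The case against.** The strongest reply is that the protocol already answers the question. Dosing can resume only if it has stopped, and the resumption clause is not limited to the first two subjects. The only obstacle is the word higher, and section 3 uses next higher dosage group and next dosage group for the same gate. The Figure 3 caption, which covers all five groups, makes the move to the next group conditional on no group holding rule being met. This stands as evidence of intent: a pause was very probably meant. But the clause presupposes a pause without ordering one, and the caption concerns starting a group, not interrupting it.

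A second reply is that the two mandatory sentences are complementary, not contradictory: 9.5.3 covers the subject's own group, and 9.5.4 adds later groups for the first two subjects. That reading is fair, but it confirms the gap for subjects 3 to 5.

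A third reply is practical. The study is single-site, the PI and local safety monitor hear first, the PI can suspend at once, and the grade 3 rule gives more than 48 hours' warning. All of this stands, and it keeps the point minor.

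A reader might go further and infer that the protocol lets group 5 dosing continue after a serious event, or that subjects were exposed to this gap. The documents support neither. Several parties can stop dosing at any time, an ad hoc SMC review is required, and section 13.2 reports no grade 3 adverse events or serious adverse events in groups 1 to 4 when group 5 was added.

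**Conclusion.** The concern holds as a minor inconsistency. The mandatory hold on later groups depends on which subject meets the rule, and for subjects 3 to 5 of group 4 no sentence clearly requires group 5 to pause. What is missing is an obligation; the power to pause exists.

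The conclusion rests on group 5 being dosed while group 4 events can still be reported, which Table 2 permits. No exact day window is claimed: the day-84 visit has a margin of 5 days either way (Table 3), 9.4.5 has events reported until the last patient visit, and Table 2 sets only lower limits on the intervals. No event probability is claimed either. The SMC charter also carries holding rules (9.5.3); it was not available and may settle the matter. Since groups 1 to 4 had been dosed by this version, the practical reach is group 5 only.

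**What to change.** Make three wording changes.

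1. In 9.5.4, replace the sentence triggered by the first two subjects with: *If a holding rule is met in any group at any time during the study, all further TB31F administration in that group and in every other group, including group 5, is held until the SMC has completed its review.* Keep the grade 3 rule counted within a group, as now, so that events in different groups are not added together. Add no day-84 limit.
2. Align the hold sentence in 9.5.3 with it.
3. In the resumption clause, change *the next higher dosage group* to *any subsequent group*.

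Check the SMC charter and align it if it differs. The changes add no subjects, tests or analyses, and leave causality with the investigators. The cost is a possible short dosing pause while the existing SMC reviews the event, and submission of the wording as a protocol amendment under 12.3.

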Escalation to the next higher dosage group will be dependent upon no safety signals arising as outlined in section 9.5.4 and will follow the same staggered algorithm as shown in figure 3. The SMC will review the safety data up to day 7 before proceeding to the next dosage group. The data to be reviewed before each dose escalation group includes the safety data (solicited and unsolicited AEs through day 7 post TB31F administration; see section 9.5.4) and clinically significant laboratory tests collected at 24 hours, 2 and 7 days following TB31F administration for all subjects in the specified dose group.

The decision to proceed at these defined time points to the next dosing group will be made by the study team upon the recommendation of the Safety Monitoring Committee (SMC) after reviewing the clinical and safety lab data available. Safety follow-up and collection of serum samples for pharmacokinetic and pharmacodynamic measurements will be done at following times: 0 hours, end

of infusion (EOI), 1, 3, 6 and 24 hours after product administration, and on days 2, 7, 14, 21, 28, 56 and 84 after product administration. Extra follow-up visits 4 and 10 days after administration for collection of serum/plasma for pharmacokinetic and pharmacodynamic measurements will be performed in group 5 (section 8.3.18). All subjects will be followed for approximately 84 days after mAb TB31F administration.

Table 1. Study groups

Study groups	Number of subjects	Single Dose	
		Mtb31F	Administration Route
Group 1	5	0.1 mg/kg	intravenous
Group 2	5	1 mg/kg	intravenous
Group 3	5	3 mg/kg	intravenous
Group 4	5	10 mg/kg	intravenous
Group 5	5	100 mg	subcutaneous

[figure not shown]

Figure 3 – Staggered dosing trial design for monoclonal antibody TB31F administration

For group 1, all subjects will receive a single dose of TB31F with a window of at least 48 hours. For groups 2-5, subject 1 and subject 2 will receive a single dose of TB31F with a window of at least 48 hours. Subjects 3, 4 and 5 of the same group will receive the same dose of mAb TB31F minimally 48 hours after subject 2. Escalation to the next dosage group will occur if no Group Holding Rules are met and upon review by the SMC.

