3.1 Visit intervals

Permissible Within-Group visit intervals

The permissible intervals for TB31F administration between subjects enrolled in all groups are indicated in table 2. The permissible study visit intervals are indicated in table 3.

Table 2. Group intervals for Visit 2 (TB31F administration)

	Interval	Optimal length of interval	Allowed interval
Group 1	Subject 001 to Subject 002	2 days	≥ 2 days
	Subject 002 to Subject 003	2 days	≥ 2 days
	Subject 003 to Subject 004	2 days	≥ 2 days
	Subject 004 to Subject 005	2 days	≥ 2 days
Subject 005 to Subject 006 (Interval between Group 1 to Group 2)		~14 days	≥ 14 days
Group 2	Subject 006 to Subject 007	2 days	≥ 2 days
	Subject 007 to Subject 008	2 days	≥ 2 days
	Subject 008 to Subject 009	1 hour	≥ 1 hour
	Subject 009 to Subject 010	1 hour	≥ 1 hour
Subject 010 to Subject 011 (Interval between Group 2 to Group 3)		~14 days	≥ 14 days
Group 3	Subject 011 to Subject 012	2 days	≥ 2 days
	Subject 012 to Subject 013	2 days	≥ 2 days
	Subject 013 to Subject 014	1 hour	≥ 1 hour
	Subject 014 to Subject 015	1 hour	≥ 1 hour
Subject 015 to Subject 016 (Interval between Group 3 to Group 4)		~14 days	≥ 14 days
Group 4	Subject 016 to Subject 017	2 days	≥ 2 days
	Subject 017 to Subject 018	2 days	≥ 2 days
	Subject 018 to Subject 019	1 hour	≥ 1 hour
	Subject 019 to Subject 020	1 hour	≥ 1 hour
Subject 020 to Subject 021 (Interval between Group 4 to Group 5)		~14 days	≥ 14 days
Group 5	Subject 021 to Subject 022	2 days	≥ 2 days
	Subject 022 to Subject 023	2 days	≥ 2 days
	Subject 023 to Subject 024	1 hour	≥ 1 hour
	Subject 024 to Subject 025	1 hour	≥ 1 hour

Table 3. Permissible study visit intervals

Interval	Type of visits	Day of Visit	Allowed interval
Visit 1	Screening	-84 to -1	-84 to 0 days
Visit 2	Inclusion	Day -1	- 4 days
Visit 3	Administration	Day 0	\pm 6 hours
Visit 4	Follow-up	Day 1	\pm 6 hours
Visit 5	Follow-up	Day 2	\pm 6 hours
Visit 5a*	Follow-up	Day 4	\pm 1 day
Visit 6	Follow-up	Day 7	\pm 1 day
Visit 6a*	Follow-up	Day 10	\pm 1 day
Visit 7	Follow-up	Day 14	\pm 2 days
Visit 8	Follow-up	Day 21	\pm 2 days
Visit 9	Follow-up	Day 28	\pm 2 days
Visit 10	Follow-up	Day 56	\pm 5 days
Visit 11	(end-of-study visit)	Day 84	\pm 5 days

* Visits 5a and 6a will only be performed in group 5

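### Protocol 9.5.4 gives no working automatic hold for a non-serious grade 3 event in the sentinel subjects

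*Protocol*

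**What the plan says.** - **Triggers (Protocol 9.5.4).** The within-group rules open with a sentinel condition: "If either of the first two subjects within a group meet a holding rule", the rest of that group and later groups are held. Two triggers follow. The first is a single SAE at least possibly related to TB31F. The second needs two or more subjects in the group with a grade 3 event "possibly, probably or definitely related to TB31F administration and persisting at grade 3 for >48 hours".
- **Spacing.** For groups 2-5 the Figure 3 legend (Protocol 3) says "Subjects 3, 4 and 5 of the same group will receive the same dose of mAb TB31F minimally 48 hours after subject 2". In Table 2 (Protocol 3.1) the group 5 row "Subject 022 to Subject 023" gives 2 days as both the optimal and the minimum gap. For the last three subjects, 9.5.3 asks for "at least a one hour interval in administration of TB31F between the completion of TB31F administration in one subject" and the start of the next.
- **Default.** If no holding rule is met, "administration of TB31F to all subjects within each dosage group will continue without any external (SMC) review" (9.5.3).
- **Release of a hold.** Dosing stops "until the SMC has completed its review and made a recommendation on trial progress" (9.5.3) and "may resume only if the local safety monitor, PI, SMC and the sponsor agree it is safe to resume TB31F administration" (9.5.4).
- **Local safety monitor (9.5.1).** The monitor takes part in reviewing severe and serious events. The explicit notice requirement covers only grade 3 events that are probably or definitely related and have lasted more than 48 hours.
- **Discretion.** 9.5.4 also allows a hold at any time on the advice of the monitor, the investigators, the SMC or the METC.

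The risk table in 6.4.1 lists the 48-hour spacing of the two sentinels as mitigation, and repeats it in the update made before group 5.

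**The concern.** A sentinel scheme needs a defined event in the first subjects that stops the next dose. Here the lead-in reads as though one sentinel's event could do that, but the only trigger one subject can meet is the related SAE. A non-serious grade 3 event, such as injection-site pain that stops daily activities (Table A1), starts no automatic hold, and 9.5.3 then lets dosing go on without SMC review.

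Group 5 is where this still matters. It is the first subcutaneous use of TB31F in humans, and no later group follows in which a lesson could be applied. At stake is the exposure of subjects 3-5 to a local reaction already seen in a sentinel, with the decision to wait left to individual judgement.

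**Working it through.** The plan gives no operating figure for the holding rule. Its only design figure (Protocol 4.4) reproduces: with n=20, 1-(1-0.1087)^20 = 0.900 and (1-0.0052)^20 = 0.901. It does not bear on this rule.

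**Step 1: count.** The non-serious rule needs at least two subjects. With one affected sentinel the count is 1, so the rule is not met at any spacing. The lead-in can therefore apply only to the one-SAE rule.

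**Step 2: timing when both sentinels are affected.** Measure hours from subject 1's dose, at Table 2 spacing: subject 1 at 0, subject 2 at 48, subject 3 at 96. Suppose subject 1 already qualifies and subject 2's event starts t hours after dosing. Subject 2 qualifies only after 48 + t + 48 = 96 + t h. Acting before subject 3 would need t < 0, which is impossible. Subject 3 cannot supply the second event in time either, since the earliest is after 96 + 48 = 144 h.

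For later subjects, let d be the administration time and count the one-hour gap from completion. Subject 4 is due at 96 + d + 1 and subject 5 at 96 + 2d + 2. The values of d for groups 2-4 come from Appendix 2. Injection time in group 5 is not given and is taken as 0.

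| Group | d (h) | Subject 4 due (h) | Subject 5 due (h) | Rule can act before subject 4 / 5 only if |
|---|---|---|---|---|
| 2 | about 1 | 98 | 100 | t < 2 / t < 4 h |
| 3 | up to 1.5 | 98.5 | 101 | t < 2.5 / t < 5 h |
| 4 | about 2 | 99 | 102 | t < 3 / t < 6 h |
| 5 | 0 | 97 | 98 | t < 1 / t < 2 h |

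In group 1 every gap is at least 48 h, so subject 4 is due at 144 h and the rule could still act there. Protocol 13.2 shows groups 1-4 already dosed, so only the group 5 row can still be acted on.

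**Step 3: would wider spacing be enough?** The gap from subject 2 to subject 3 must exceed 48 + t: more than 54 h for onset at 6 h, and more than 72 h for onset at 24 h. Two affected subjects would still be required.

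**Step 4: notice and observation.** For an event in subject 2, the 9.5.1 notice also waits until after 96 + t h. It leaves out the possibly related events that 9.5.4 counts. Table 3 allows subject 2's Day 2 visit at 48 h plus or minus 6 h, so subject 3 can be dosed before it takes place.

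**Step 5: relative weight of the two cases.** The documents give no event rate. Purely as an assumption, let each sentinel independently have probability p of a qualifying event. At least one affected is 1-(1-p)^2 and both affected is p^2. For p = 5% these are 9.75% and 0.25%; for p = 20%, 36% and 4%. The one-sentinel case in Step 1 is the commoner one.

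**The case against.** The strongest reply is that the protocol does not leave subjects unprotected:

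- A hold on advice is available at any time, and the PI, monitor, SMC, METC or PATH may suspend use.
- Subjects are told to call for severe symptoms (8.3.5), and severe complaints are assessed immediately by a clinician (9.2.1).
- The SAE definition includes other important medical events on the investigator's judgement (9.2.3), so some grade 3 events could meet the one-SAE rule.
- Unexpected laboratory abnormalities are repeated. Poor subcutaneous tolerance can be met by 1:1 dilution and extra sites (5.1).
- No grade 3 AE or SAE occurred in 20 intravenous subjects at up to 10 mg/kg. Group 5's absorbed dose is about 0.56 mg/kg (100 × 0.5 / 90) to 1.6 mg/kg (100 × 0.8 / 50), using the weights and bioavailability in 6.5.
- The 48-hour filter keeps out brief events such as clemastine fatigue. Fatigue of grade 1 or 2 on the dosing day occurred in 12 of 20 (13.2).

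Much of this stands, and it limits the harm. It does not supply a trigger: nothing obliges anyone to act on a defined non-serious event, and dilution is optional and is not a hold. The intravenous experience says little about local tolerance of a subcutaneous injection.

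A reader might infer that the protocol contains no hold at all for such an event. The documents do not support that; what is missing is an automatic hold. Nor is the 2-day spacing the reason why one sentinel's event fails to stop dosing. The subject count is the reason, and the spacing matters only when both sentinels are affected.

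**Conclusion.** The point holds in a limited form. For non-serious grade 3 events, 9.5.4 has no automatic trigger that one sentinel can meet. The two-subject trigger cannot act before subject 3 at the planned and minimum spacing. In group 5 it can act before subjects 4 and 5 only if subject 2's event starts within about 1 or 2 hours of dosing and subject 1 also qualifies.

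This rests on 2-day gaps being used (longer ones are allowed, with no upper limit in Table 2) and on a negligible injection time. The SMC charter, which 9.5.3 also cites for holding rules, was not seen and may contain more. The remaining exposure is mainly local tolerability in up to three group 5 subjects. That makes it a modest safety correction, worth making before group 5 is dosed; it does not suggest that earlier groups were handled unsafely.

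**What to change.** 1. **9.5.4: add a sentinel pause, separate from the holding rules.** Proposed text: *If subject 1 or subject 2 of a group has an AE of grade 3 or higher that is at least possibly related to TB31F, dosing of all subjects in that group not yet dosed pauses until the local safety monitor has reviewed the event, within 2 working days, and agrees with the PI to continue. The monitor may release the pause at once for a brief event explained by premedication, such as clemastine fatigue.* Two working days is the limit 9.5.3 already sets for SMC review. Keep the two-subject, more-than-48-hour rule for the whole group, and limit the sentinel lead-in to the pause and the one-SAE rule.
2. **Consequential wording.** Make the 9.5.3 default conditional on no pause being in force. State that SMC review and four-party agreement apply to the holding rules and not to release of the pause. Align the SMC charter if it repeats the rule.
3. **9.5.1: notice.** Notify the monitor of these sentinel events, including possibly related ones, without waiting 48 hours.
4. **Table 2: a note.** Complete subject 2's Day 2 visit before subject 3 is dosed.

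**Cost.** The amendment needs a favourable METC opinion before use (12.3); the documents do not say how long that takes. Group 5 may be delayed by a few days, and some pauses will be for transient or premedication-related events. A pause over a weekend could outlast the 4-day inclusion allowance in Table 3, so some subjects might need a repeat inclusion visit with its blood and urine tests.
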